12.10.7. Pharmacokinetic Tables

Pharmacokinetic: Tables					
No.	Population	IDSL / Example Shell	Title	Programming Notes	Deliverable [Priority]
Secondary: Pharmacokinetic					
4.01.	PK		Summary of GSK3772847 Serum Pharmacokinetic Concentration-Time Data (ug/ml)		SAC
4.02.	PK		Summaries of the Incidence of and Titres of Anti-GSK3772847 Antibodies		SAC

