2.2. Study Objective(s) and Endpoint(s)

Objectives	Endpoints
Primary Objectives	Primary Endpoints
To evaluate the efficacy of 3 doses of GSK3772847 (administered every 4 weeks) compared with placebo in moderate to severe asthma participants with allergic fungal airway disease (AFAD) who are currently on Standard of Care (SoC)	
 Change from baseline (Week 0) in blood eosinophils over time Change from baseline (Week 0) in fractional exhaled nitric oxide (FeNO) over time
Secondary Objectives	Secondary Endpoints
To evaluate the serum pharmacokinetics (PK) of 3 doses of GSK3772847 (administered every 4 weeks) in moderate to severe asthma participants with AFAD	
 Serum concentrations of GSK3772847
To evaluate the pharmacodynamics (PD) of GSK3772847 in moderate to severe asthma participants with AFAD	
 Serum levels of free and total soluble suppressor of tumorigenicity 2 (sST2)
To evaluate the levels and specificity of any anti-drug antibodies formed following dosing with GSK3772847	
 Incidence and titres of serum anti- GSK3772847 antibodies
To evaluate the health status of moderate to severe asthma participants with AFAD currently on SoC, and who are treated with GSK3772847 compared with placebo-treated participants	
 Change from baseline (Week 0) in Asthma Control Questionnaire -5 (ACQ-5) absolute score at Weeks 2, 4, 8 and 12 Change from baseline (Week 0) in Asthma Quality of Life Questionnaire (AQLQ) total and domain scores at Weeks 2, 4, 8 and 12 Proportion of responders to ACQ-5. A responder to

Objectives	Endpoints
	
ACQ-5 will be defined as a subject who has a decrease from baseline in ACQ-5 score of 0.5 or more at Weeks 2, 4, 8 and 12.
 
 • Proportion of responders to AQLQ. A responder to AQLQ will be defined as a subject who has an increase from baseline in AQLQ score of 0.5 or more at Weeks 2, 4, 8 and 12.
To evaluate the effect on lung function of moderate to severe asthma participants with AFAD currently on SoC, treated with GSK3772847 compared with placebo	
 • Change from baseline (Week 0) in spirometry parameters over time including but not limited to pre-bronchodilator Forced expiratory volume in 1 second (FEV1).

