4. ANALYSIS POPULATIONS

4.1. Analysis Populations

Population	Definition / Criteria	Analyses Evaluated
Enrolled	The All Subjects Enrolled (ASE) population will consist of all participants who sign the ICF.	
 • Study population • Subjects by country and site ID • Age ranges • Screening/run-in status and reason for screening/run-in failure.
Screened	The screened population will consist of all participants who sign the ICF, but who did not pass the screening/run-in criteria and therefore were not randomised.	
 • Reasons for screen/run-in failure
Randomised	The randomised population will consist of all participants who were randomised. A participant who is recorded as a screen or run-in failure and also randomised will be considered to be randomised in error provided they have not performed any study assessments.	
 • No formal analysis will be performed on this population
Modified Intent-to-Treat	
 • The modified Intent-to-Treat (mITT) will consist of all randomised participants who take at least 1 dose of study treatment. • Participants will be analysed according to the treatment they receive $\geq 50\%$ of the time. If the participant receives 50% of each treatment they will be analysed according to the randomised treatment. 	
 • Study population • Inclusion, exclusion and randomisation criteria deviations • Participant disposition • Efficacy

Population	Definition / Criteria	Analyses Evaluated
Safety	This population will be the same as the Modified Intent-to-Treat population.	
 • Safety
Pharmacokinetic	The PK population will consist of all randomised participants who received at least one dose of study medication, and for whom at least one pharmacokinetic sample was obtained, analysed and was measurable.	
 • PK

Refer to [Appendix 10](#): List of Data Displays which details the population used for each display.

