5.2. Baseline Definitions

For all endpoints (except as noted in baseline definitions) the baseline value will be the latest pre-dose assessment with a non-missing value, including those from unscheduled visits. If time is not collected, Day 1 assessments are assumed to be taken prior to first dose and used as baseline.

Parameter	Study Assessments Considered as Baseline			Baseline Used in Data Display
	Screening	Run-in	Day 1 (Pre-Dose)	
Primary Endpoints				
Fractional Exhaled Nitric Oxide (FeNO)	X		X	Day 1
Blood Eosinophils	X		X	Day 1
Other Patient Reported Outcomes				
AQLQ			X	Day 1
Asthma Control Questionnaire (ACQ-5) score	X		X	Day 1
Spirometry				
Forced Expiratory Volume (FEV1)	X		X	Day 1
Pharmacodynamics				
Free and total sST2 (serum)			X	Day 1

Parameter	Study Assessments Considered as Baseline			Baseline Used in Data Display
	Screening	Run-in	Day 1 (Pre-Dose)	
Safety				
Vital Signs	X	X	X	Day 1
12-lead Electrocardiogram (ECG) measurements	X		X	Day 1
24 hours Holter measurements		X	X	Day 1
Clinical laboratory tests (haematology and chemistry)	X		X	Day 1
Immunogenicity: Anti-GSK3772847 antibodies			X	Day 1
Biomarkers				
Induced sputum biomarkers		X	X	Run-in ¹
Exploratory serum markers (including IgE and Fungal-specific IgE)	X		X	Day 1

NOTES:

- Unless otherwise stated, the mean of replicate assessments taken on the same day will be used as the value for that day.
- ¹ Baseline is taken at run-in. If the sputum taken at run-in is not viable then a sample is taken at Day 1 (Pre-Dose) and is used as baseline.

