8. SAFETY ANALYSES

The safety analyses will be based on the Safety population, unless otherwise specified. The details of the planned displays are provided in [Appendix 10: List of Data Displays](#).

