8.4. Antibodies

Summaries of the incidence of and titres of anti- GSK3772847 antibodies at weeks 0*, 2, 4*, 8*, 12 and 24.

* = Pre-dose only

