9.1. Secondary Pharmacokinetic Analyses

Serum concentrations of GSK3772847 will be summarised by nominal time.

Pharmacokinetic summaries will be based on the Pharmacokinetic population, and no intercurrent events will be considered.

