Free and total sST2 (serum)			X ¹	X	X ²	X ¹	X ³	X ³	1. Pre and Post Dose 2. Pre Dose 3. Anytime (± 5 days) Pre-dose samples: within 2 hours from the planned dosing time Post-dose samples as soon as possible after end of infusion but must be taken within 4 hours.
Total & fungal specific IgE	X ¹		X ²	X	X	X	X		1. Fungal specific IgE only if no historical documented results available 2. Pre-dose

Procedure	Screening (±5days)	Run-in (±5days)	Treatment Period (Visit window ±3days)				End of Treatment / EW (±3days)	FU (±3days)	Notes
			V3	V4	V5	V6			
Visit	V1	V2	V3	V4	V5	V6	V7	V8	
Week	-4	-2	0	2	4	8	12	24	
Induced sputum sample for biomarkers		X	X ¹²				X ³		
 1. If no viable sample is produced at V2, induction should be repeated pre dose at V3 2. If a participant does not produce a viable baseline sputum sample at visit 2 or at visit 3, the participant will not need to undergo a sputum induction at the end of the treatment period. 3. If no viable sample is produced, induction should be repeated after a minimum of 72 hrs but no later than 7 days after scheduled visit.

Procedure	Screening (±5days)	Run-in (±5days)	Treatment Period (Visit window ±3days)				End of Treatment / EW (±3days)	FU (±3days)	Notes
			V3	V4	V5	V6			
Visit	V1	V2	V3	V4	V5	V6	V7	V8	
Week	-4	-2	0	2	4	8	12	24	
Pharmacokinetics									
Serum blood sample for PK			X ¹	X	X ²	X ³	X ⁴	X ⁴	1. Post Dose 2. Pre Dose 3. Pre and Post Dose 4. Anytime (± 5 days) Pre-dose samples: within 2 hours from the planned dosing time Post-dose samples as soon as possible after end of infusion but must be taken within 4 hours.
Safety									
Laboratory assessments	X ^{1,2}		X ^{1,3}	X ¹	X ^{1,3}	X ¹	X ^{1,3}	X ¹	1. Clinical chemistry (includes liver chemistry) 2. Routine urinalysis at screening (Visit 1) 3. Cardiac markers Note: haematology assessments in efficacy section
Serum blood sample for immunogenicity			X ¹	X	X ¹	X ¹	X	X	1. Pre Dose

Procedure	Screening (±5days)		Treatment Period (Visit window ±3days)				End of Treatment / EW (±3days)	FU (±3days)	Notes
	V1	Run-in (±5days)	V3	V4	V5	V6	V7	V8	
Week	-4	-2	0	2	4	8	12	24	
Urine or serum pregnancy test (WOCBP only)	X ¹		X		X	X	X	X	To be performed pre-dose during the treatment period 1. Serum pregnancy test required
12-lead ECG	X		X ¹		X ¹	X ¹	X		1. Test to be performed pre-dose and post-dose within 30 mins after end of infusion.

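### The only anti-drug antibody table (Table 4.02) is run on the PK population, which in practice empties its placebo column

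*SAP*

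**What the plan says.** Section 2.2 makes the incidence and titres of serum antibodies to GSK3772847 a secondary endpoint, under the objective "To evaluate the levels and specificity of any anti-drug antibodies formed following dosing with GSK3772847".

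Section 8.4 carries this out: "Summaries of the incidence of and titres of anti- GSK3772847 antibodies at weeks" 0, 2, 4, 8, 12 and 24, with pre-dose samples on dosing days. It names no population. The opening of Section 8 gives the default: "The safety analyses will be based on the Safety population, unless otherwise specified".

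Appendix 10 (Section 12.10.7) lists the display as Table 4.02, "Summaries of the Incidence of and Titres of Anti-GSK3772847 Antibodies", files it under the secondary pharmacokinetic tables and enters PK in the population column. Section 4.1 defines that population as randomised, dosed participants "for whom at least one pharmacokinetic sample was obtained, analysed and was measurable".

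**The concern.** A subject who receives only placebo has no GSK3772847 to measure, so the measurability condition removes the placebo arm from the only table of a stated secondary endpoint. Nothing in Sections 4.1, 8.4 or 9.1 says that this was intended.

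What is lost is the concurrent reference. Antibody assays can give positives in people who never had the drug. The Week 0 pre-dose sample shows reactivity that active subjects already had. It cannot show how often new positives appear after baseline without drug, whereas placebo subjects followed over the same visits can.

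There is also a lesser weakness. Entry to the table depends on a post-dose result, measurable drug, and antibodies can themselves affect that result. That makes it a poor condition for an immunogenicity denominator, even if few active subjects would be lost.

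**Working it through.** The SAP gives no figure to reproduce, so the check is a cross-reading followed by a count.

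**How the SAP classifies antibodies**

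| Place | Treatment of antibodies |
|---|---|
| 5.2, baseline table | "Immunogenicity: Anti-GSK3772847 antibodies" is in the Safety block, with a Day 1 pre-dose baseline |
| 8 and 8.4 | Under Safety Analyses; the default is the Safety population |
| 12.2.1, schedule | "Serum blood sample for immunogenicity" is under Safety, with no restriction by arm |
| 9.1 | Covers serum concentrations and does not mention antibodies; "Pharmacokinetic summaries will be based on the Pharmacokinetic population" |
| 12.10.7, Table 4.02 | Under pharmacokinetic tables; population PK |

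**Who is in each population (4.1)**

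- Safety is the same as mITT: all randomised subjects with at least one dose, in both arms.
- PK is the dosed subjects with at least one measurable concentration. The expected placebo count is 0. The exceptions would be a subject analysed as placebo who was given a misallocated active dose, or an assay artefact.

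**Is the endpoint shown elsewhere?** None of safety tables 3.01 to 3.12 and none of listings 1 to 48 names antibodies.

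**Scheduled results missing from Table 4.02**

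- Antibody time points per subject (8.4 and schedule): Weeks 0, 2, 4, 8, 12, 24 = 6. After baseline: 6 − 1 = 5.
- Number randomised: Section 2.1 says that the 20 randomised subjects needed for the internal safety review were not reached, so at most 19.
- The allocation ratio is not given in the SAP. Three ratios are assumed:

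| Assumed active:placebo | Placebo subjects | Scheduled results (× 6) |
|---|---|---|
| 1:1 | 19/2 = 9.5, about 10 | about 60 |
| 2:1 | 19/3 = 6.3, about 6 | about 36 |
| 3:1 | 19/4 = 4.75, about 5 | about 30 |

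These are upper bounds. They take 19 as randomised and assume that every subject was dosed and attended every visit.

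**Loss in the active arm**

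PK samples per subject (schedule): Week 0 post-dose 1 + Week 2 1 + Week 4 pre-dose 1 + Week 8 pre- and post-dose 2 + Week 12 1 + Week 24 1 = 7. An active subject leaves the table only if all 7 are missing, unanalysed or unmeasurable. The first is due within 4 hours of the end of the first infusion, so this loss is likely negligible.

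**The case against.** The strongest reply is that no rule is broken. Section 8 allows exceptions to its default, Section 4.1 leaves the population of each display to Appendix 10, and Appendix 10 is explicit. A programmer has one clear instruction. This stands, and it is why the point is an inconsistency and a poor choice rather than a contradiction. It permits the choice but gives no reason for it.

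The second reply is that the objective concerns antibodies formed after active dosing and names no placebo comparison, whereas the health-status, lung-function and safety objectives do. An active-only table would fit that wording. But the pharmacodynamic objective on soluble ST2 names no placebo comparison either, and Section 10.1 and Tables 6.01 and 6.02 summarise it on mITT, which covers both arms. By the SAP's own practice, the missing comparison does not imply an active-only display.

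Three smaller points are fair:

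- Section 4.1 lists only PK as the use of the PK population, but that column is not exhaustive: the mITT row omits pharmacodynamics. Little weight should rest on it.
- Section 9.1 agrees with the table entry once the table is labelled pharmacokinetic, so it does not decide the matter.
- Listing 25 (laboratory data with character results, Safety population) might contain antibody results; the SAP does not say. The safe claim is that placebo results are absent from Table 4.02. A listing would not in any case supply the incidence and titre summary that Section 8.4 calls for.

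**Conclusion.** The concern holds, at minor severity. Followed as written, the only summary of a secondary endpoint would have an empty placebo column, although the schedule collects these samples without distinction by arm and the body of the SAP treats them as safety data. Each placebo subject loses 6 scheduled time points from the table. The totals of about 30 to 60 rest on the assumed allocation ratios and on the ceiling of 19 randomised, and actual numbers may be lower.

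The exclusion of placebo subjects is inferred from the measurability condition and is not a stated rule. The inference is safe apart from a misallocated dose or an assay artefact. The consequence is limited: the study stopped early, everything is descriptive, pre-existing reactivity in active subjects remains visible at Week 0, and almost no active-arm data are lost.

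**What to change.** In Appendix 10, change the population of Table 4.02 from PK to Safety and present it by treatment group, keeping the Week 0 pre-dose baseline already set in Section 5.2. Add a sentence to Section 8.4 naming the Safety population, so that text and display list agree. Keep the PK population for Table 4.01.

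If an active-only display was intended, Section 8.4 should say so and give the reason. That would remove the inconsistency but not restore the placebo reference.

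The cost is one cell and one sentence. No further samples or assays are needed beyond those already scheduled.

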12.10.8. Pharmacodynamic and Biomarker Tables

Pharmacodynamic and Biomarker: Tables					
No.	Population	IDSL / Example Shell	Title	Programming Notes	Deliverable [Priority]
Secondary Pharmacodynamic: Free and Total SST2					
6.01.	mITT		Summary of Raw and Percentage Change from Baseline in Free Soluble ST2 concentration (ug/mL) (On-treatment)		SAC
6.02.	mITT		Summary of Raw and Percentage Change from Baseline in Total Soluble ST2 concentration (ng/mL) (On-treatment)		SAC

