10. PHARMACODYNAMIC AND BIOMARKER ANALYSES

10.1. Secondary Pharmacodynamic Analyses

Summary statistics of raw and percentage change from baseline in free and total soluble ST2 levels (serum) will be produced.

Pharmacodynamics summaries will be based on the mITT population, and no intercurrent events will be considered.

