12.2. Appendix 2: Schedule of Activities

12.2.1. Protocol Defined Schedule of Events

Procedure	Screening (±5days)	Run-in (±5days)	Treatment Period (Visit window ±3days)				End of Treatment / EW (±3days)	FU (±3days)	Notes
			V3	V4	V5	V6			
Visit	V1	V2	V3	V4	V5	V6	V7	V8	
Week	-4	-2	0	2	4	8	12	24	
Day	-28	-14	1	15	29	57	85	169	
Informed consent	X								May be obtained prior to Screening.
Inclusion and exclusion criteria	X	X	X						Recheck clinical status before 1 st dose of study medication.
Demography	X								
Full physical examination	X								To include height and weight
Medical/medication/ drug/alcohol/smoking history	X								Including smoking history, substance abuse, medical conditions and family history of premature cardiovascular disease; asthma disease duration and exacerbation history
Human immunodeficiency virus (HIV), Hepatitis B and C screening	X								If test otherwise performed within 3 months prior to first dose of study treatment, testing at screening is not required
Genetics									
Informed consent for Pharmacogenetic blood sample		X							

Procedure	Screening (±5days)	Run-in (±5days)	Treatment Period (Visit window ±3days)				End of Treatment / EW (±3days)	FU (±3days)	Notes
			V3	V4	V5	V6			
Visit	V1	V2	V3	V4	V5	V6	V7	V8	
Week	-4	-2	0	2	4	8	12	24	
Pharmacogenetic (PGx) blood sample			X						PGx sample may be drawn any time from Visit 3 onwards, pre-dose. Informed consent must be obtained before collecting a sample.
Study Treatment and Questionnaires									
Randomisation			X						
Study treatment			X		X	X			
Dispense diary card		X							To be completed daily.
Diary card review			X	X	X	X	X		
Collect diary card							X		
Rescue medication dispensing		X	X ¹	X ¹	X ¹	X ¹			1. As needed
ACQ-5	X		X	X	X	X	X		Test to be performed before all other assessments
AQLQ			X	X	X	X	X		Test to be performed immediately after ACQ-5
Efficacy									
Haematology (including eosinophil count)	X		X ¹	X	X	X	X		1. Pre-dose
FeNO	X		X	X	X	X	X		Test to be performed pre-dose
Spirometry	X		X	X	X	X	X		Test to be performed pre-dose

Procedure	Screening (±5days)	Run-in (±5days)	Treatment Period (Visit window ±3days)				End of Treatment / EW (±3days)	FU (±3days)	Notes
			V3	V4	V5	V6			
Visit	V1	V2	V3	V4	V5	V6	V7	V8	
Week	-4	-2	0	2	4	8	12	24	

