12.4. Appendix 4: Study Phases and Treatment Emergent Adverse Events

12.4.1. Study Phases

Assessments and events will be classified according to the time of occurrence relative to study treatment start date.

Study Phase	Definition
Pre-Treatment	Date ≤ Study Treatment Start Date
On-Treatment	Study Treatment Start Date < Date ≤ Study Treatment Stop Date + 28 days
Post-Treatment	Date > Study Treatment Stop Date + 28 days

Completion of study epochs will be defined as the following:

Study Phase	Definition of Completion
Run-in	Randomised into study and received first dose of study treatment
Treatment	Completed Week 12 visit
Follow up	Completed 12 week follow-up period

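### The only planned sST2 tables are limited to On-treatment, which leaves every scheduled Week 24 sample out of all displays and leaves the status of Week 12 unsettled

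*SAP*

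**What the plan says.** Section 2.2 makes serum levels of free and total sST2 a secondary endpoint and sets no time limit. Section 10.1 sets none either: "Summary statistics of raw and percentage change from baseline in free and total soluble ST2 levels (serum) will be produced".

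The list of displays narrows this. In section 12.10.8, Table 6.01 is titled "Summary of Raw and Percentage Change from Baseline in Free Soluble ST2 concentration (ug/mL) (On-treatment") and Table 6.02 is titled "Summary of Raw and Percentage Change from Baseline in Total Soluble ST2 concentration (ng/mL) (On-treatment").

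Section 12.4.1 gives the phase rule. It applies to assessments as well as to events: "Assessments and events will be classified according to the time of occurrence relative to study treatment start date". On-Treatment is "Study Treatment Start Date < Date ≤ Study Treatment Stop Date + 28 days".

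The schedule in section 12.2.1 numbers the visit days as "Day -28 -14 1 15 29 57 85 169". Study treatment is given at Weeks 0, 4 and 8. sST2 is drawn at those visits and at Weeks 2, 12 and 24. The note for Weeks 12 and 24 reads "3. Anytime (± 5 days").

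**The concern.** A scheduled time point of a secondary endpoint would be collected and then reported nowhere. The restriction appears only in the two table titles. Table 1 in section 2.1, which records what was dropped after early termination, keeps the secondary endpoints and does not mention removing follow-up sST2. The neighbouring displays are not limited in this way. The PK concentration table (4.01) has no On-treatment label, although PK is also sampled at Weeks 12 and 24, and section 8.4 runs the antibody summaries to Week 24. The report could therefore show drug concentration and antibodies at Week 24 without the matching target measurement.

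A second problem is that the 28-day limit ends exactly on the nominal Week 12 day. Two programmers following different sections of the SAP could produce different Week 12 rows from the same data.

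**Working it through.** **Inputs (all from the SAP).**
- Last planned dose: Week 8, Day 57, window ±3 days, so Days 54 to 60 (12.2.1).
- Week 12: Day 85. The visit window is ±3 days (Days 82 to 88). The sST2 sample window is ±5 days (Days 80 to 90).
- Week 24: Day 169. With ±5 days, Days 164 to 174.
- On-Treatment limit: stop date + 28 days, inclusive (12.4.1).

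The SAP gives no figure of its own to reproduce. The check is gap = sample day − last dose day, and a sample is On-Treatment if gap ≤ 28. This takes the stop date to be the last dose date, which the SAP does not state.

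**Week 24.**
- Nominal gap: 169 − 57 = 112 days.
- Smallest: 164 − 60 = 104. Largest: 174 − 54 = 120.
- All exceed 28, so 100% of scheduled samples are excluded.
- Earlier stopping widens the gap. With a last dose on Day 29 it is 169 − 29 = 140 days.
- If the stop date instead meant last dose + 28 days, the limit would be 28 + 28 = 56 days. The smallest gap, 104, still exceeds it.

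**Week 12, with phase assigned by actual date.**
- Nominal gap: 85 − 57 = 28 days, exactly on the inclusive limit. It is kept, but with no slack.
- Range with the ±3-day window: 82 − 60 = 22 to 88 − 54 = 34 days.
- Range with the ±5-day window: 80 − 60 = 20 to 90 − 54 = 36 days.
- A sample is lost when its offset from Day 85 exceeds the dose offset from Day 57. Counting over dose offsets −3 to +3:
  - ±3 days: 6+5+4+3+2+1+0 = 21 of 7 × 7 = 49 pairs, or 42.9%.
  - ±5 days: 8+7+6+5+4+3+2 = 35 of 7 × 11 = 77 pairs, or 45.5%.
- These percentages assume independent, uniform visit days. A triangular spread centred on the nominal day gives 41.4% and 43.4%. If every visit falls on its nominal day the loss is 0%. If every sample is late relative to the Week 8 dose it is 100%.
- A participant who missed the Week 8 dose has a limit at Day 29 + 28 = Day 57 and would lose Week 12 altogether, provided the stop date is the last dose date.

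**Week 12, on the other readings.** Section 12.5.2 uses planned time relative to dosing for summaries unless otherwise stated, and section 12.3.1 uses nominal visits without windowing. On planned time the gap after a Week 8 dose is exactly 28 days, so Week 12 stays in. If the stop date meant last dose + 28, the limit of 56 exceeds the largest gap of 36, and again no Week 12 sample is lost after a Week 8 dose.

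**Listings.** None of Listings 1 to 48 names sST2. Listings 33 and 34 cover eosinophils and FeNO. Listing 24 depends on normal ranges, and the SAP gives none for sST2. Listing 25 is for laboratory results in character form.

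**The case against.** The strongest reply concerns Week 12. Planned time (12.5.2) and nominal visits (12.3.1) both keep it. The schedule heads that visit as end of treatment, and section 12.4.1 counts the treatment epoch as complete at the Week 12 visit. The stop date is not defined: section 12.4.2 uses last dose date instead, and section 12.6.2 treats each dose as covering 28 days. A literal filter would also place the Day 1 samples outside the tables, because Pre-Treatment is "Date ≤ Study Treatment Start Date". That would include the baseline itself, so the label may be a loose name for the treatment period. This stands to the extent that a Week 12 loss is possible but not established. It does not remove the ambiguity, because the wording on time of occurrence in 12.4.1 may count as an exception to 12.5.2, and the SAP names no order of precedence.

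A reader might infer that nearly half of completers lose Week 12, or that about 4 of 9 participants per arm do. The documents do not support either. The percentages need an assumed spread of visit days. Section 2.1 says only that 20 randomised subjects were not reached, and the SAP states neither the number randomised nor an allocation ratio. A reader might also infer that the Week 24 sample was meant to show sST2 returning off drug, but the SAP states no purpose for it.

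It can also be said that all outputs are descriptive, that the study was not to inform internal decisions, and that section 10.1 is silent on time points rather than in conflict with the titles. These points limit the consequence. They do not restore Week 24, which lies outside a treatment-period label as well. Section 12.7.1 would include all available planned data, but only unless otherwise specified, and the titles specify otherwise. Its promise to list the data of withdrawn participants has no matching sST2 listing.

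**Conclusion.** The point holds fully for Week 24 and conditionally for Week 12. With the restriction applied, all scheduled Week 24 sST2 samples are excluded from the only two tables, whether by actual date, by planned time or under either meaning of stop date, and no listing shows them.

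For Week 12 the finding is an unresolved rule. Samples taken more than 28 days after the last dose drop out only if phase follows actual date and the stop date is the last dose date. The possible loss is then 0 to 100%, with 43 to 45% as an illustration under uniform visit days. No measured loss is claimed.

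The weight is moderate. The endpoint is secondary and descriptive, but a whole scheduled time point goes unreported in a study that had already stopped short of 20 randomised subjects.

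**What to change.** Delete the On-treatment restriction from the titles of Tables 6.01 and 6.02. State in section 10.1 that free and total sST2 are summarised by nominal visit and time point at Week 0 (pre- and post-dose), Weeks 2 and 4, Week 8 (pre- and post-dose), and Weeks 12 and 24, with Week 24 labelled as follow-up. Add a listing of all sST2 values to section 12.10.

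This restores Week 24 and also settles Week 12, because inclusion no longer depends on the phase rule or on the meaning of stop date. The cost is two titles, one programming filter, one sentence and one listing, with no new data.
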